8.1.2.2. Conjunctival Redness

Conjunctival redness will be graded from 0 to 3. This is a clinical assessment to evaluate the severity of redness. For the overall CAS assessment, Grade 0 and 1 are considered absent (and should receive a score of ‘0’ in the CAS scoring) and Grade 2 or 3 are considered present (and should receive a score of 1 in the CAS scoring).

Grade 0 – none

Grade 1 – mild: equivocal redness

Grade 2 – moderate: defined redness, <50% redness excluding plica and caruncle

Grade 3 – severe: >50% redness excluding plica and caruncle

The same assessor should conduct the evaluation at each visit for the full duration of the study. Instructions will be provided in a study manual.

8.1.2.3. Eyelid Swelling

Eyelid swelling will be graded from 0 to 3. This is a clinical assessment to evaluate the severity of lid swelling. For the overall CAS assessment, Grade 0 and Grade 1 below are considered absent (and should receive a score of '0' in the CAS scoring) and Grade 2 and 3 are considered present (and should receive a score of "1" in the CAS scoring).

Grade 0 – none

Grade 1 – swelling very superficial, changed appearance like thickened skin

Grade 2 – definite swelling but no lower eyelid festoons, and in the upper eyelid, the skin fold becomes angled fold on 45° downgaze

Grade 3 – lower eyelid festoons or upper lid fold remains rounded on 45° downgaze

The same assessor should conduct the evaluation at each visit for the full duration of the study. Instructions will be provided in a study manual.

8.1.2.4. Chemosis

Chemosis will be graded from 0 to 3. This is a clinical assessment to evaluate the severity of chemosis. For the overall CAS assessment, Grade 0 is considered absent (and should receive a score of '0' in the CAS scoring) and Grade 1, 2 or 3 are considered present (and should receive a score of 1 in the CAS scoring).

Grade 0 – None

Grade 1 – Conjunctiva looks pale and loses transparency

Grade 2 – Bulging of conjunctiva

Grade 3 – Chemosis prevents appropriate palpebral closure

The same assessor should conduct the evaluation at each visit for the full duration of the study. Instructions will be provided in a study manual

8.1.3. Lid Aperture

Distance between the lid margins in mm with the patient looking in the primary position, sitting relaxed and with distant fixation. Margin reflex distance 1 (MRD1) and MRD2 parameters will be measured. The same assessor should conduct the evaluation at each visit for the full duration of the study. Instructions will be provided in a study manual.

8.1.4. Lagophthalmos, Eyelid Retraction, and Von Graefe's Sign

Presence or absence of lagophthalmos and Von Graefe's sign will be recorded.

Eyelid retraction is a displacement of the upper eyelid superiorly or lower eyelid inferiorly.

Instructions will be provided in a study manual.

8.1.5. Assessment of Diplopia and Extraocular Movements

Bahn-Gorman Scale for Diplopia

- Grade 0 – Normal
- Grade I – Intermittent diplopia: present only when patient is fatigued
- Grade II – Inconstant diplopia: present only on lateral or upward gaze
- Grade III – Constant diplopia: present on straight and level gaze and correctable with prisms
- Grade IV – Constant diplopia: present on straight and level gaze but not correctable with prisms

Duction Testing for Extraocular Movements

- Assessment of extraocular movements in all 4 primary directions (up, down, nasal and temporal) will be performed.

The same assessor should conduct the evaluation at each visit for the full duration of the study. Instructions will be provided in a study manual.

8.1.6. Orbital MRI

Axial high-resolution images will be obtained locally and transmitted to a central radiology vendor for review. Besides assessment of proptosis, the orbital MRI sequences may provide (but not limited to) volumetric analysis of eye compartments such as muscle and fat, and assessment of inflammation in the orbit as well as any damage to the optic nerve. Further instructions will be provided in a study manual. Patients who cannot have an MRI due to the presence of metal or other known reason may participate in the study without having the MRI scans. In the US only, an orbital CT scan may be performed if the patient cannot have an MRI scan.

8.1.7. Facial Digital Photographs

External photographs of the eyes that capture at minimum the five cardinal positions of gaze (up, down, right, left and primary gaze) may be taken at the study sites and transmitted to a central reading vendor for review. The study will only use the 5 cardinal directions of gaze for evaluation. The whiteness of the sclera, MRD1, MRD2, and eye movement will be assessed from the digital photographs to confirm the clinical assessment including CAS, lid retraction, and eye movement measurements. Further instructions will be provided in a study manual.

8.2. Safety Assessments

An SRC will be formed for periodic reviews of safety and available PK and PD data. For the randomized, double-blind treatment arms, the SRC will review masked data. The SRC will be minimally composed of the Medical Monitor, at least 1 study PI, and at least 1 independent member with expertise in the treatment of TED. In cases where the SRC determines that an unexpected or critical finding requires expert opinion or access to unmasked data, the SRC may refer the question to at least 3 independent experts selected by the Sponsor, including the SRC

Chair, to assess the situation by reviewing necessary unmasked data and provide recommendation back to the SRC. The SRC charter will describe the committee member structure and details for the conduct and safety review meetings.

Safety will be assessed throughout the study by examination of visual acuity, visual fields, and color defects; TEAEs; changes in concomitant medications; and changes from Baseline in clinical laboratory evaluations, vital signs, 12-lead ECGs, ophthalmic assessments, and physical examinations. Safety assessments by visit are listed in [Table 1](#). Safety monitoring ([Section 10.1.6.1](#)) and reporting ([Section 8.3](#)) are summarized. Additional safety assessments may occur at the discretion of the PI (or designee).

Any ongoing study drug-related SAEs or severe TEAEs present at the time of study termination will be followed until resolved or until the event stabilizes and the overall clinical outcome has been ascertained. All other TEAEs considered related to study drug and SAEs considered not related to study drug will be followed for 30 days after the EOS/ET visit or after the last dose of study drug, whichever is later.

In the event of unexplained, treatment-emergent, clinically significant, abnormal laboratory values or clinically significant changes in laboratory values from Baseline, the laboratory tests should be repeated immediately and followed until the values have returned to within the reference range or to Baseline.

8.2.1. Best Corrected Visual Acuity, Visual Fields, and Color Defects

Change of best corrected visual acuity by ≥ 3 lines (15 words) at 4m on the ETDRS chart, new or increased visual field (by Humphrey field testing) or color defects (Ishihara test) may require additional assessments. If a different measure or assessment is used, it must be approved by the Medical Monitor and equivalent criteria used for assessment. Instructions will be provided in a study manual.

8.2.2. Slit Lamp Biomicroscopy and Intraocular Pressure

Slit lamp biomicroscopy and intraocular pressure (IOP) should be performed with each ophthalmic exam.

8.2.3. Dilated Fundoscopy

Dilated fundus exam will be assessed by the fundus ophthalmoscopy after dilation of the right eye and the left eye.

8.2.4. Physical Examinations

Complete physical examination includes general appearance, head, ears, eyes, nose, throat, dentition, thyroid, chest (heart, lungs), abdomen, skin, neurological, extremities, back, neck, musculoskeletal, and lymph nodes.

Brief examinations are limited, symptom-directed, physical examinations as clinically indicated.

8.2.5. Body Weight

The study site staff should use a digital precision scale if possible and record the weight in kilograms or pounds to the first decimal point (eg, 95.3 kg). The same scale should be used, and the patient should wear a standard hospital-type gown or equivalent light clothing and no shoes for the body weight measurement.

8.2.6. Vital Signs

Vital sign measurements in this study will include seated respiratory rate, blood pressure, pulse rate, and body temperature. Vital signs should be measured after the patient rests for approximately 5 minutes in a sitting position. If infusion-associated events occur during the infusion, vital signs will be checked every 5 minutes until stable, then every 15 minutes for two more checks. Additionally, vital signs will be monitored every 15 minutes from the start of the infusion until 60 minutes after its completion for any subsequent infusions following previous immediate or delayed infusion-associated events.

8.2.7. ECGs

Perform triplicate ECGs within a 15-minute period, separated by ≥ 1 minute. ECG recordings will be taken after ≥ 5 minutes in a semi-supine, quiet-rest position (head of bed between 0° and 90°), and before obtaining any blood sample.

The results of all 12-lead ECGs (heart rate, QTcF, PR interval, RR interval, QRS interval) will be recorded to the eCRF.

If the 12-lead ECG must be performed with the patient in another position (eg, sitting, standing), the PI (or designee) should record the alternative position. The PI (or designee) should date and sign the ECG tracing and record the clinical significance of any abnormal result on the tracing. ECGs will be interpreted by a qualified physician (the PI or designee).

8.2.8. Clinical Safety Laboratory Tests

Procedures for obtaining, processing, shipping, and handling laboratory specimens will be detailed in the Laboratory Manual.

Clinical laboratory tests include chemistry, hematology, coagulation, UA, urine drug screen, and additional tests listed in Appendix 2, [Section 10.2](#).

The PI (or designee) will evaluate all Screening and safety laboratory reports and will sign and date the review. Any out-of-range laboratory results should be assessed for clinical significance. The PI (or designee) should follow all clinically significant laboratory abnormalities occurring during the study that were not present at Baseline as needed. These abnormalities should be evaluated with additional tests, if necessary, until the underlying cause is diagnosed, event becomes stable or resolution occurs. The diagnosis and resolution date must be reported to the Sponsor via the eCRF.

8.2.9. Pregnancy Testing

WOCBP must have a negative serum pregnancy test at Screening, a negative urine pregnancy test on Day 1, and be willing to undergo additional pregnancy tests, as required, throughout the study. WOCBP will have urine pregnancy tests predose on dosing days and a serum pregnancy test at the EOS/ET visit.

Serum FSH levels will be tested in women at Screening and must be in the menopausal range to confirm postmenopausal status.

8.3. AEs, SAEs, and Other Safety Reporting

The definitions of AEs and SAEs are provided in Appendix 3, [Section 10.3](#).

8.3.1. Time Period and Frequency for Collecting AE and SAE Information

Detection and recording of AEs and SAEs starts from the signing of the ICF until the Day 365/Week 53 visit. From this visit to the EOS visit, only treatment-related AEs/SAEs will be recorded. AEs that occur after signing the ICF, but before the first dose of study drug, will be recorded to the eCRF as medical history, unless related to a study procedure. Detection and recording of TEAEs will start at the time of the first dose of study drug. Any SAE that occurs after signing the ICF (before or after the first dose of study drug) will be recorded to the eCRF as an SAE.

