- Lid aperture, visual acuity, diplopia and extraocular movements, lid retraction, lagophthalmos, Von Graefe's sign, slit lamp biomicroscopy, and intraocular pressure should be assessed predose on dosing days
- Visual fields should be assessed predose on dosing days. In the event of elevated IOP or AEs potentially related to decreased optic nerve function, additional visual fields may be assessed at PI discretion.
- Ishihara color vision assessment should be assessed predose on dosing days
- Exception: Patients who cannot have an MRI due to the presence of metal or other known reason. In the US only, an orbital CT scan may be performed in patients who cannot have an MRI. In such cases all imaging time points must have a CT scan performed. Images collected within 30 days of consent as part of standard of care may be used as the Baseline scan, provided that the acquired image conforms to the study-specific image acquisition parameters and with prior approval from the Medical Monitor.

- m. Randomization will take place by IRT after all eligibility criteria are met and not more than 3 days before dosing
- n. Safety laboratory samples should be obtained predose
- o. PK samples should be obtained predose on the specified dosing days in the schedule of assessments above. On Days 1 and 337, samples should also be obtained 30-60 minutes after the end of the infusion. On Day 344, the sample should be collected at a similar time of day when the Day 337 post dose sample collection occurred.
- p. ADA samples should be obtained predose on the specified dosing days in the schedule of assessments above. On Day 1, samples should also be obtained at end of infusion (≤ 60 minutes after the end of the infusion).
- q. Blood samples for exploratory biomarkers relevant to TED, fibrosis, and inflammation should be collected predose on the specified dosing days in the schedule of assessments above.
- r. Serum for analysis of IL-11 and IL-11R should be obtained predose on the specified dosing days in the schedule of assessments above. On Days 1 and 337, serum samples should also be obtained 30-60 minutes after the end of the infusion.
- s. Treatment-emergent adverse events should be captured until Week 53 (Day 365). From this visit to the EOS/ET (Week 73: Day 505) visit, only treatment-related AEs should be recorded.

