9.2.5. Safety Analyses

Safety will be assessed in the Safety Analysis Population.

Safety will be evaluated by presenting listings and summaries of AEs, vital signs, 12-lead ECGs, ophthalmic assessments, conventional clinical laboratory evaluations (serum chemistry, hematology, coagulation, and UA evaluations), prior and concomitant medication use, treatment compliance, and exposure. Safety variables will be tabulated by treatment arm, LASN01 dose level and placebo. Other safety measures (eg, physical examination findings, pregnancy test results, drug screening test results) will be listed.

AEs will be coded using the MedDRA version 24.1 or higher. The incidences of TEAEs will be presented by system organ class and preferred term according to MedDRA, by relationship to the study drug, by severity, and by whether or not they resulted in alteration of administration of or discontinuation of study drug. A TEAE is defined as an AE that occurs during or after the first study drug infusion. A TRAE is defined as an AE with a plausible temporal relationship between the onset of the AE and administration of study drug (and as further defined in [Table 6](#)). TEAEs will be captured until Day 365/Week 53. From this visit to the EOS visit, only TRAEs will be recorded. In addition, the incidences of serious TEAEs and TEAEs leading to discontinuation of study drug will be presented by system organ class, preferred term, and relationship to study drug.

Descriptive statistics and change from Baseline for clinical laboratory test and vital sign results will be presented by scheduled time point. Incidences of potentially clinically significant clinical laboratory results, determined based on normal ranges, will also be summarized by scheduled time point. The numbers and percentages of abnormal 12-lead ECGs will be provided by scheduled time point.

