10.3.2.1. SAE Definition Clarifications

- Death is an outcome of an AE, and not an AE in itself
- All deaths during study drug infusion or occurring up to the EOS/ET visit, regardless of cause or relationship, must be reported
- “Occurring at any dose” does not imply that the patient is actively receiving study drug at the time of the event

- “Life-threatening” means that the patient was at immediate risk of death from the event as it occurred. This does not include an event that might have led to death, had it occurred with greater severity.
- Complications that occur during hospitalizations are AEs. If an AE prolongs hospitalization, it is an SAE.
- “In-patient hospitalization” means the patient has been formally admitted to a hospital for medical reasons, for any length of time. This may or may not be overnight. It does not include presentation and care within an emergency department (although an emergency department visit may define a medically important event, which is also considered an SAE).
- The PI (or designee) should attempt to establish a diagnosis of the event based on signs, symptoms, and other clinical information. In such cases, the diagnosis should be documented as the AE or SAE, rather than as the individual signs or symptoms.

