10.3.4. Reporting of SAEs

The Sponsor has requirements for expedited reporting of SAEs meeting specific criteria to regulatory authorities. Therefore, the Sponsor must be notified immediately regarding any SAE

that occurs after administration of the study drug and any SAE assessed by the PI (or designee) as related to a study procedure that occurs after the participant has signed an ICF.

All SAEs must be reported to the Medical Monitor within 24 hours of the Investigational Site's knowledge of the event. The study site will transmit a SAER using the designated safety mailbox.

An optional initial report can be made via telephone, but a completed SAER must still be faxed or emailed within 24 hours of the site's knowledge of the event. The Investigational Site will be provided with SAER forms wherein the following information is requested. In addition, relevant eCRF pages should be appended to communicate relevant study drug and patient outcome information.

- Patient identification number, PI name, and site number
- SAE information: event term, onset date, severity, and causal relationship
- The outcomes attributable to the event (eg, death, a life-threatening AE, inpatient hospitalization, prolongation of existing hospitalization, a persistent or significant disability or incapacity, or other important medical event[s])
- A summary of relevant test results, pertinent laboratory evaluations, and any other relevant medical history
- The first and last dates of study drug administration. NOTE: as this is a double-masked study, SAERs should not indicate specific study drug assignments
- Indicate if the study drug was discontinued or the study drug administration schedule modified
- Supplemental information may include the following hospital records: laboratory results, radiology reports, progress notes, admission and emergency room notes, holding and observation notes, discharge summaries, autopsy reports, and death certificates

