12.1 Adverse Events

Treatment-emergent adverse events (TEAEs) are defined as any event that occurs or worsens by clinically meaningful amount on or after the first dose of study drug administration. Only TEAEs will be summarized, however all AEs collected in the eCRF will be presented in data listings. All AEs will be coded using the Medical Dictionary for Regulatory Activities (MedDRA) version as specified in the DMP.

An overall summary will be presented that includes the number of events and the number and percentage of patients who experienced at least one TEAE by treatment arm and overall for all patients. This summary will also include breakdowns of TEAEs further categorized as ocular or non-ocular, serious TEAEs, related TEAEs, TEAEs leading to early treatment discontinuation, TEAEs leading to early study discontinuation, TEAEs leading to death, and Serious TEAEs by maximal severity.

Additional summaries of TEAEs classified by MedDRA SOC and PT will be provided showing the number of events and the number and percentage of patients who experienced at least one TEAE by treatment arm and overall for all patients. If a patient reports multiple TEAEs to the same SOC or multiple PTs within the same SOC, the patient will be counted only once within that SOC or PT. In the summaries, SOC and PTs within the SOC will be listed in descending frequency order for the All Patients column.

Separate summaries by SOC and PT will be provided for the following categories of AEs:

- TEAEs

CONFIDENTIAL

The contents of this document are confidential to [REDACTED]
Unauthorized use, disclosure, or reproduction is strictly prohibited.

- Related TEAEs
- TEAEs by maximal severity grade
- Serious TEAEs by maximal severity grade
- Related TEAEs by maximal severity grade

The number of patients with any TEAEs (along with percentages) will be tabulated by SOC and PT within each SOC by treatment arm and overall for all patients. To count the number of patients with any TEAEs, if a patient has multiple TEAEs coded to the same SOC or PT within an SOC, the patient will be counted once under the maximum severity.

All TEAEs will be presented in a patient listing. In addition, serious TEAEs, related TEAEs, and TEAEs leading to death will be listed separately.

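### After Week 53 the protocol gives conflicting collection rules for SAEs and deaths, and the SAP's all-causality TEAE tables run across the change without an end date

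*Protocol*

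**What the plan says.** **The restriction.** Protocol Section 8.3.1 starts AE and SAE recording at consent and runs it to the Day 365 (Week 53) visit. From there to end of study, "only treatment-related AEs/SAEs will be recorded". Two other places state the limit with a different scope. Footnote s to the Schedule of Activities (Section 1.3) says "From this visit to the EOS/ET (Week 73: Day 505) visit, only treatment-related AEs should be recorded". Section 9.2.5 says "TEAEs will be captured until Day 365/Week 53" and then "From this visit to the EOS visit, only TRAEs will be recorded". Neither of these names SAEs.

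**The rules without a causality limit.**
- Section 8.3.1, last sentence: "Any SAE that occurs after signing the ICF (before or after the first dose of study drug) will be recorded" on the eCRF as an SAE.
- Section 10.3.2.1: "All deaths during study drug infusion or occurring up to the EOS/ET visit, regardless of cause or relationship, must be reported".
- Section 10.3.4: "the Sponsor must be notified immediately regarding any SAE" after dosing, and every SAE goes to the Medical Monitor within 24 hours. No Week 53 limit is given.

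**The analysis.** SAP 12.1 counts as a TEAE any event that starts, or worsens to a clinically meaningful degree, from the first dose onward, with no end date. It states: "Only TEAEs will be summarized, however all AEs collected in the eCRF will be presented in data listings". The summaries include all TEAEs, serious TEAEs and TEAEs leading to death, all regardless of causality, with separate tables for related TEAEs. SAP 12.1 does not mention the change in collection at Week 53.

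**The concern.** Safety is a primary objective. If the protocol gives two answers on whether an unrelated SAE after Week 53 is recorded, two sites can each follow the text and return different data. In a trial of about 24 randomized patients, one SAE or death that is handled differently changes the safety record.

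The second problem is in the tables. A column headed TEAE should reflect one collection rule. Here it would include all events up to Day 365, but after that only events that passed an investigator's causality judgement. A reader of the SOC/PT or severity tables could not see this from SAP 12.1.

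**Working it through.** **1. The plan's own figure.** The synopsis gives 24 weeks of follow-up from the last dose (Day 337) to end of study (Day 505). (505 − 337)/7 = 168/7 = 24.0 weeks, so it reproduces.

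**2. Length of the restricted window, for a patient given all 13 doses.**
- Day 365 to Day 505: 505 − 365 = 140 days (20 weeks).
- Share of post-dose follow-up: 140/168 = 83.3%.
- Share of time on study: 140/(505 − 1) = 140/504 = 27.8%. All-causality collection covers the other 364/504 = 72.2%.

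**3. The same cut for a patient given fewer doses.** SAP 3.1 and 3.2.1 allow 7 to 13 doses. On the four-weekly schedule the seventh dose falls on Day 1 + 6 × 28 = 169. If that patient is followed to Day 365, full recording lasts 365 − 169 = 196 days after the last dose, against 365 − 337 = 28 days after a thirteenth dose. The 83.3% in step 2 does not describe such a patient.

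**4. The rules side by side, for an event after Day 365 judged unrelated.**

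| Event | 8.3.1 restriction | 8.3.1 last sentence | 10.3.2.1 | 10.3.4 |
|---|---|---|---|---|
| Non-serious AE | not recorded | silent | silent | silent |
| SAE | not recorded | recorded | silent unless fatal | notified within 24 hours |
| Death | not recorded if the fatal SAE is judged unrelated | recorded as an SAE | reported | notified within 24 hours |

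The first row has no conflict. The second and third do. The conflict inside Section 8.3.1 is recording against recording, and no order of precedence is given.

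**5. Which SAP tables are affected.** Related TEAEs are collected to end of study under one rule, so the Related TEAE tables are consistent throughout. The all-causality tables (overall, SOC/PT, by severity) mix the two rules for non-serious events. They also mix them for serious events if sites apply the Section 8.3.1 restriction to SAEs.

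**6. Possible number of SAEs concerned.** The documents give neither an event rate nor the number of patients who passed Day 365, so both are assumptions here. Expected unrelated SAEs m = patients × rate × 140/365.25; the chance of at least one = 1 − exp(−m).

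| Assumed rate per patient-year | All 24 followed through the window | 8 followed through the window |
|---|---|---|
| 0.05 | m = 0.46, chance 37% | m = 0.15, chance 14% |
| 0.10 | m = 0.92, chance 60% | m = 0.31, chance 26% |
| 0.20 | m = 1.84, chance 84% | m = 0.61, chance 46% |

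The column for 24 patients is the upper end for the randomized arms, because the study stopped early.

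**The case against.** The strongest reply is that the conflict is narrower than it looks. The last sentence of Section 8.3.1 follows a rule on pre-dose events, and Section 10.3.3.1 restates it for pre-dose SAEs only, so it may be mainly a classification rule. Section 10.3.2.1 can be read as a specific override for deaths. Section 10.3.4 governs notification to the sponsor, which is a different act from eCRF recording. This stands in part: a site that follows Sections 10.3.2.1 and 10.3.4 still sends these events to the sponsor. It does not remove the conflict. The sentence in Section 8.3.1 expressly covers events after the first dose, and the restriction there expressly names SAEs.

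Sections 8.2 and 10.3.3.4 require follow-up of unrelated SAEs beyond end of study. They are not clearly a further contradiction, since they can apply to SAEs recorded before Week 53 and still ongoing.

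It could also be said that Section 9.2.5 already ends TEAE capture at Day 365. But its own TEAE definition has no end date, the SAP says that its methods supersede the protocol's, and SAP 12.1 carries no cut-off.

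A reader might draw stronger conclusions that the documents do not support:
- *That SAEs or deaths have been lost.* This needs a site to disregard Sections 10.3.2.1 and 10.3.4. The documents do not show that any did.
- *That the comparison between arms is biased.* The rule is the same in every randomized arm, investigators stayed masked until database lock (SAP Section 16), and Table 6 of the protocol treats an event as related unless the criteria for unrelated are met.
- *That incidences cannot be compared between patients who stopped at different times.* That is largely ordinary unequal follow-up, which uniform collection would not remove.
- *That full recording stops too soon for the drug's half-life.* No passage ties AE collection to half-lives, related events are collected to end of study, and the 28-day gap assumes all 13 doses.

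**Conclusion.** The point holds for SAEs and deaths after Week 53. The protocol passages disagree on whether an unrelated event is captured, and the three statements of the restriction differ on whether it covers SAEs at all. Limiting non-serious AEs to related ones is a permissible design choice that nothing else contradicts.

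It also holds for the SAP's all-causality TEAE and serious TEAE tables, which have no end date and so span two collection rules. The Related TEAE tables are sound.

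The restricted window is 140 of 168 post-dose days, assuming all 13 doses with the last on Day 337 and follow-up to Day 505. SAP Section 1 reports that many patients did not reconsent to the latest protocol version and that the study ended early, so few may have entered the window and the effect on the final tables may be small. The documents do not give the number, and they do not show it to be zero. No power or alpha figure is touched.

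**What to change.** 1. **Protocol.** Reconcile Section 8.3.1, footnote s in Section 1.3 and Section 9.2.5 with Sections 10.3.2.1 and 10.3.4, so that SAEs and deaths have one collection rule to end of study that does not depend on causality.
2. **SAP 12.1.** Limit the all-causality TEAE tables to onset up to Day 365. Keep the Related TEAE tables to end of study; cutting them too would drop late events that were collected consistently. List later events separately, labelled with the collection rule that applied.
3. **Before database lock.** Query sites for any SAE or death after Week 53 that was left unrecorded.

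The cost is a protocol clarification, a short SAP addition, a short site query and perhaps a few more unrelated SAEs in the listings. No visit is added, since AE evaluation is already scheduled on Days 379, 393, 449 and 505. If early termination leaves the protocol change with little prospective use, the SAP text and the query still apply.
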